7.7 Concomitant Medical Therapy

7.7.1 Pre PCI medication

Aspirin. Preloading with aspirin 300 to 325 mg at least 2 hrs before the PCI is mandatory. For patients already receiving chronic aspirin therapy, the loading dose of 300 to 325 mg of aspirin should still be given. Either regular or chewable tablets or intravenous aspirin is mandatory for the loading dose in patients not on chronic aspirin before the ULMCA PCI.

ADP antagonists. ADP antagonist pre-loading therapy is mandatory. The choice of one of the followings agent is left to the discretion of the investigator. For patients already receiving chronic ADP antagonist therapy, pre-loading is still mandatory.

- clopidogrel 300-600 mg before PCI (even if patient is on chronic clopidogrel therapy); or
- at sites in countries where it is approved and is commercially available prasugrel 60 mg >1 hr before PCI; or ticagrelor 180 mg >1 hr before PCI.

Pre-PCI statin therapy. Optimal medical therapy with strict control of LDL (target of ≤ 1.8 mmol/l) is strongly recommended, along with optimization of all medical therapy – rosuvastatin/atorvastatin (according to the guidelines). Several randomized trials have demonstrated that high dose statin therapy decreases PCI-related myonecrosis in patients undergoing stent implantation, whether or not the patient is already taking chronic statin therapy^{37, 38 39 40}. Therefore, in the absence of absolute contraindications to statin use (e.g. severe allergy with prior use), at least one dose of the following statin regimens should be administered before the PCI (within 12 hours), regardless of LDL level and history of prior statin use.

- atorvastatin 80 mg daily
- rosuvastatin 40 mg daily

Other medications. The use of other medications prior to PCI (e.g. beta-blockers, ACE inhibitors) is left to the discretion of the treating physicians.

7.7.2 Intra-procedure adjunctive pharmacology

During the procedure, patients should receive bolus and maintenance doses of unfractionated heparin to avoid excess coagulation. The currently recommended target activated clotting time (ACT) is at least > 250 sec during coronary angioplasty. If Angiomax® (bivalirudin) is used instead of heparin an ACT does not need to be measured or recorded. Refer to the package insert for bivalirudin for indications, contraindications, warnings and precautions.

In patients who do not receive Glycoprotein (GP) IIb/IIIa inhibitors, a weight-adjusted unfractionated heparin bolus (70 to 100 IU per kg) will be administered to achieve a target ACT of > 250 sec. In patients who receive GP IIb/IIIa inhibitors, a weight-adjusted unfractionated heparin bolus (50 to 70 IU per kg) will be administered to achieve a target ACT of > 200 sec. Post-procedural heparin infusions are not recommended during GP IIb/IIIa therapy. The currently recommended target ACT for eptifibatide and tirofiban is less than 300 sec during coronary angioplasty.

GP IIb/IIIa inhibitors are strongly discouraged in patients adequately pre-loaded with an ADP antagonist (clopidogrel, prasugrel, or ticagrelor), especially if bivalirudin is used.

7.7.3 Post-procedural Medication Regimen

Antiplatelet therapy

Please refer to the specific package insert for clopidogrel, prasugrel or ticagrelor for indications, contraindications, warnings and precautions. Chronic daily ADP antagonist therapy is mandated for at least one year after PCI. The choice of agent is left to the discretion of the investigator, local standard of care and drug availability.

All patients must receive a maintenance dose of clopidogrel 75 mg/day. In case of prasugrel the maintenance dose is 10 mg/day (the dose of prasugrel may be decreased to 5mg/day in patients with a weight <60 kg or age >75 years) or in case of ticagrelor the maintenance dose is 90 mg bid.

Note1: prasugrel and ticagrelor have no label for elective PCI.

A daily ADP antagonist must be given for at least one year in the absence of major complications, and is recommended for the duration of the trial in the absence of major bleeding or other complications. ADP antagonists should not be discontinued within the first year after DES implantation unless absolutely necessary for major bleeding, major trauma, or major surgery necessitating discontinuation of antiplatelet therapy (e.g. intracranial surgery). Many surgeries can safely be performed while the patient is on dual antiplatelet therapy. If a patient on dual antiplatelet therapy requires surgery, strong consideration should be given to performing the surgery without antiplatelet agent discontinuation. If a particular dual antiplatelet therapy must be discontinued, a GP IIb/IIIa bridging strategy up until the time of surgery may be considered, followed by reloading of the ADP antagonist as soon as possible post surgery.

Aspirin

Following the PCI procedure, all patients should continue on aspirin (minimum of 75 mg/day up to 162 mg/day or dose per standard hospital practice) indefinitely.

Aspirin should not be discontinued for CABG or other reasons unless absolutely necessary.

Note2: avoid maintenance doses of aspirin above 100 mg daily for patients prescribed to ticagrelor.

All DAPT (including start and stop times of interrupted DAPT) and other cardiac medications will be recorded for data collection at each visit. Extended DAPT will be at the discretion of the

investigator.

7.8 Hospital Discharge (post-PCI to hospital discharge)

At discharge, from the hospital where the index procedure took place, an assessment of angina status and cardiovascular drug use will be performed. Any Serious Adverse Events will be recorded and an ECG will be performed. The patient must be informed of the required DAPT medication and follow-up visits per protocol should be scheduled prior to discharge.

In addition, CK-MB (preferred) or Troponin (cTn) if CK-MB is not available, in the post-procedure hospitalization period should be taken at 12 hrs (± 2 hrs; i.e. 10-14 hrs) and 24h (± 2 hrs; i.e. 22-26 hrs) post procedure or at discharge if sooner.

If cardiac enzymes are elevated (CKMB >3 ULN, or cTn/hs-cTn >35 ULN), serial measurements of cardiac enzymes must be taken until a decline is noted. In any case of cardiac enzyme elevation (CK >2ULN with iso-enzyme CKMB, CKMB >3 ULN, or cTn/hs-cTn >35 ULN) at least two samples (with an preferred interval of 6 hours) should be obtained prior to discharge.

Additional serial troponins or CK-MBs should be drawn at any time in case of any adverse cardiac event.

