⁵ CK-MB (preferred), or Troponin (cTn) if CK-MB is not available, are drawn within 24 hours prior to the start of the PCI procedure. Blood can be withdrawn from the arterial sheath prior to the index procedure.

For patients showing elevated Troponin (e.g. non-STEMI patients) at baseline (within 24h pre-PCI) an additional blood sample must be collected prior to the PCI procedure to confirm that:

- hs-cTn or Troponin I or T levels are stable, i.e. the value should be within 20% range of the value found in the first sample at baseline, or have dropped
- CK-MB and CK levels are within normal range

If hs-cTn or Troponin I or T levels are stable or have dropped, the CK-MB and CK levels are within normal ranges, and the ECG is normal, the patient may be included in the study.

⁶ CK-MB (preferred), or Troponin (cTn) if CK-MB is not available, are determined within 10-14 hours and 22-26 hours post-procedure or at discharge if sooner. If cardiac enzymes are elevated (CK >2ULN with iso-enzyme CKMB, CKMB >3 ULN, or cTn/hs-cTn >35 ULN), serial measurements of cardiac enzymes must be taken until a decline is noted.

⁷ iFR pre-procedure is mandatory to explore the physiological importance of the left main bifurcation disease.

ⁱⁱ IVUS assessment post-stent implantation for optimization of BiOSS LIM C deployment is highly recommended according to ESC guidelines (Class IIa, level of evidence: B)

⁷ Collect and forward to central Core Lab (material collection only).

⁸ For all intercurrent angiographies and revascularizations (incl. stent thrombosis, etc.), the angiogram must be sent to the Monitor organization and/or CRO (Cardialysis).

⁹ It is recommended to attempt achieving a residual SYNTAX Score ≤8 post PCI. A SYNTAX Score assessment post-PCI is optional for the investigators.

Note: In the event of intercurrent illnesses, interventions, adverse events, or treatment failure, effort should be made to complete the required observations as much as possible.

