Platelet transfusions should be recorded and reported but are not included in these definitions until further information is obtained about the relationship to outcomes.

If a CABG-related bleed is not adjudicated as at least a type 3 severity event, it will be classified as not a bleeding event. If a bleeding event occurs with a clear temporal relationship to CABG (i.e., within a 48-h time frame) but does not meet type 4 severity criteria, it will be classified as not a bleeding event.

*Corrected for transfusion (1 U packed red blood cells or 1 U whole blood = 1 g/dL hemoglobin).

†Cell saver products are not counted.

CABG indicates coronary artery bypass graft

DEATH

(ARC)⁴²

The deaths will be adjudicated per the ARC definition: All deaths are considered cardiac unless an unequivocal non-cardiac cause can be established. Specifically, any unexpected death even in patients with coexisting potentially fatal non-cardiac disease (e.g. cancer, infection) should be classified as cardiac.

- **Cardiac death:**

Any death due to proximate cardiac cause (e.g. MI, low-output failure, fatal arrhythmia), unwitnessed death and death of unknown cause, all study procedure related deaths including those related to concomitant treatment.

- **Vascular death:**

Death due to non-coronary vascular causes such as cerebrovascular disease, pulmonary embolism, ruptured aortic aneurysm, dissecting aneurysm, or other vascular cause.

- **Non-cardiovascular death:**

Any death not covered by the above definitions such as death caused by infection, malignancy, sepsis, pulmonary causes, accident, suicide or trauma.

MYOCARDIAL INFARCTION (MI)

EXCEL study definition

Peri/Post procedure MI:

Defined as the occurrence within 72 hours after PCI of either:

- CK-MB $\geq 10x$ ULN or cTn* (I or T) $\geq 70x$ ULN,
- OR: CK-MB $\geq 5x$ ULN or cTn* (I or T) $\geq 35x$ ULN in combination with any of the following:
 - new pathological Q waves in at least 2 contiguous leads or new persistent non-rate related LBBB, or
 - angiographically documented native coronary artery occlusion or new severe stenosis with thrombosis and/or diminished epicardial flow, or
 - imaging evidence of new loss of viable myocardium or new regional wall motion abnormality

*while EXCEL definition did not comprise cTn, we consider equivalence CK-MB $\geq 10x$ versus cTn $\geq 70x$ and CK-MB $\geq 5x$ versus cTn $\geq 35x$ ⁴³

Spontaneous MI*

Defined as the occurrence >72 hours after any PCI of:

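### Troponin is followed until decline only above 35x ULN, the lower (conditional) MI cut-off, while CK-MB is followed from 3x ULN, below its own cut-off of 5x, so some silent peri-procedural MIs could go unsampled in troponin-monitored patients

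*Combined protocol and SAP*

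**What the plan says.** **Scheduled samples.** Note 6 to the Schedule of Assessments (section 1.1) says the cardiac enzymes "are determined within 10-14 hours and 22-26 hours post-procedure or at discharge if sooner". The assay is "CK-MB (preferred) or Troponin (cTn) if CK-MB is not available" (section 7.8), so troponin is the fallback.

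**Trigger for sampling until decline.** Section 7.8: "If cardiac enzymes are elevated (CKMB >3 ULN, or cTn/hs-cTn >35 ULN), serial measurements of cardiac enzymes must be taken" until they fall. Note 6 uses the same CK-MB and troponin cut-offs but adds total CK: "If cardiac enzymes are elevated (CK >2ULN with iso-enzyme CKMB, CKMB >3 ULN, or cTn/hs-cTn >35 ULN), serial measurements of cardiac enzymes must be taken".

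**Two-sample rule.** In section 7.8, CK >2 ULN appears only in the next sentence, with the same CK-MB and troponin levels. There the requirement is that "at least two samples (with an preferred interval of 6 hours) should be obtained prior to discharge". Section 7.8 then asks for extra serial troponin or CK-MB draws after any adverse cardiac event, at any enzyme level.

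**MI definition.** Appendix I (Myocardial Infarction, EXCEL study definition) counts a peri-procedural MI within 72 hours of PCI in either of two ways:
- CK-MB at least 10x or troponin at least 70x ULN, with nothing else required.
- CK-MB at least 5x or troponin at least 35x ULN, plus new Q waves or persistent LBBB, angiographic evidence, or imaging evidence.

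Its footnote begins "while EXCEL definition did not comprise cTn, we consider equivalence CK-MB" and pairs 10x with 70x and 5x with 35x. Any MI counts in the primary endpoint (section 5.1).

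**The concern.** A trigger for sampling until decline exists so that the peak is measured. It does that for CK-MB, because sampling continues from a level below either MI cut-off. For troponin it starts only once the lower cut-off has been passed. No section explains the difference, and none requires another sample because the last value is still rising.

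Ascertainment of a primary-endpoint component then depends on which assay a site has. The study is single-arm against a fixed target, so no concurrent control arm shares the loss. Section 8.6 takes event reporting as complete up to last follow-up, so an MI that was never sampled is counted as event-free time. Adjudication cannot recover a peak that was not drawn.

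**Working it through.** **1. The plan's own figure.** Inputs from section 8.2: reference and assumed true rate 16.7%, margin 6.3 points, one-sided alpha 5%, power 80%. Target = 16.7% + 6.3% = 23.0%.

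n = [(1.645 × √(0.23 × 0.77) + 0.842 × √(0.167 × 0.833)) / 0.063]² = 255.04, rounded up to 256. This matches the stated 256 analyzable patients. The sample size does not depend on the enzyme trigger.

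**2. Trigger against MI cut-off.** Ratio from Appendix I: 35/5 = 70/10 = 7.

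| | CK-MB | Troponin |
|---|---|---|
| Trigger for sampling until decline | >3x | >35x |
| Trigger ÷ lower MI cut-off | 3/5 = 60% | 35/35 = 100% |
| Trigger ÷ stand-alone MI cut-off | 3/10 = 30% | 35/70 = 50% |

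The troponin trigger (above 35x) even sits marginally above the MI rule (35x or more). In CK-MB terms, troponin 35x is 35/7 = 5x.

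**3. Who falls in the gap.** A patient tested by troponin, with no recognised cardiac event, whose last scheduled value is 35x or less and rising. The last sample is at 22-26 h, or earlier if discharge is sooner. At 26 h, 72 − 26 = 46 h of the MI window remain. Two routes to an uncounted MI stay open:
- A silent rise to 70x or more, which is at least a doubling after the last sample and needs no supporting evidence.
- A rise to 35x or more where the supporting evidence is present but no new event prompts sampling. An example is an occlusion or diminished flow already visible on the index films.

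**4. What a missed event does to the test.** One event is 1/260 = 0.38 points. The plan uses a Kaplan-Meier upper limit. With complete follow-up, p + 1.645 × √(p(1−p)/260) stands in for it:
- 49 events: 18.85% + 3.99% = 22.84%, below 23.0%, success.
- 50 events: 19.23% + 4.02% = 23.25%, above 23.0%, failure.

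With a true rate of 23.0%, this rule (success at 49 or fewer of 260) has a one-sided error of 6.2%. If some patients have their only PoCE event missed, it becomes:
- 0.5 points missed (1.3 patients): 8.9%
- 1.0 point missed (2.6 patients): 12.3%
- 2.0 points missed (5.2 patients): about 22%

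These miss rates are assumptions; the documents give none.

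**5. What one missed event would require.** Let s be the share of patients monitored by troponin (assumed). One expected missed event needs a miss rate of (1/260)/s among them: 3.8% if s = 10%, 1.5% if s = 25%, 0.8% if s = 50%.

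**The case against.** The other side has real force on several points, and most of it stands.

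- **35x is not an MI by itself.** A reader might infer that troponin is followed only once the patient already has an MI. The documents do not support that: 35x needs supporting evidence, 70x is the stand-alone cut-off, and every value above 35x must be followed until it falls.
- **The adverse-event rule is a safeguard.** A reader might infer that a rising troponin below 35x is simply not followed. Section 7.8 requires serial sampling after any adverse cardiac event, which probably covers many patients who have the evidence needed at 35x. It does not reach a silent rise to 70x, or evidence already on the index films.
- **Troponin is the fallback.** It is used only where CK-MB is unavailable. The share could be small, and any count of missed events would rest on assumed inputs.
- **Capture weaker than in EXCEL is not shown.** A reader might infer that POLBOS LM detects fewer MIs than its benchmark did. The documents do not give EXCEL's sampling schedule or follow-up triggers. Nor do they show whether 35x/70x troponin classifies more or fewer MIs than 5x/10x CK-MB.
- **The 49-versus-50 example is generic.** Any single event decides a borderline result, and it needs an observed rate near 19% against the planned 16.7% (about 43 of 260).
- **21x is not a protocol figure.** Multiplying 3x by 7 gives 21x, but Appendix I states equivalence at two points only. A lower value is a linear extrapolation.

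None of this explains why the two assays are treated differently, and none of it closes the gap for silent rises.

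**Conclusion.** The mismatch is real and follows from the plan's own equivalence. It is limited to troponin-monitored patients without a recognised cardiac event whose last value is at or below 35x and rising. Within that group some peri-procedural MIs could be missed. The direction is certain: a missed MI leaves the observed PoCE rate unchanged or lowers it, which favours meeting 23.0%. The size is not: one event is 0.38 points, and the error rates above hold only under assumed miss rates, complete follow-up and the simple upper limit used as a stand-in.

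The CK >2 ULN difference is a separate wording contradiction. Note 6 requires sampling until decline and section 7.8 only at least two samples. Total CK is not a scheduled post-procedure assay, and no effect on the endpoint is shown.

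This is a cheap improvement in ascertainment. It is not evidence that the comparison with EXCEL is biased.

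**What to change.** Reconcile note 6 of section 1.1, section 7.8 and Appendix I in one of two ways:
- Place the troponin trigger below the 35x MI cut-off, as the CK-MB trigger lies below 5x. Linear scaling of the protocol's ratio would give about 21x, for illustration only; the sponsor sets the value.
- Require sampling until decline whenever the last value is still rising, whatever its level.

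If the present asymmetry is intended, state the reason. Use one rule for CK >2 ULN in note 6 and section 7.8.

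The cost is amendment wording, an eCRF prompt, a few extra routine blood draws in troponin-monitored patients and occasionally a later last sample. The sample size and the planned analysis do not change.

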7.9 Clinical Follow-up

Hospital visits are planned at 1 month (± 7 days) and 1 year (± 30 days). A phone contact is scheduled at 6 months (± 14 days). An assessment of the anginal status, compliance to protocol-required medications, other cardiovascular drug use and any Serious Adverse Events will be recorded during clinical follow-up visits. An ECG will be performed.

Patients with typical cardiac symptoms or evidence of progressive heart disease should in most cases undergo repeat cardiac catheterization; stress testing should not be performed, especially in the patient with possible recurrent disease in the left main stem.

Because of the risk of exercise-induced stent thrombosis, in no case should routine follow-up exercise stress testing be performed within 8 weeks after stent implantation.

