Statistical Analysis Plan	
Primary Analysis: The primary efficacy endpoint is based on comparison to pre-specified performance goal based on the PCI arm of the EXCEL study³. The study is powered at 80% to show non-inferiority of the BiOSS LIM C compared with XIENCE EES. The primary analysis will be based on an intent-to-treat (ITT) patient population.
 
Assumptions: Power = 80% One-sided alpha = 5% Non-inferiority margin of 6.3% PCI (XIENCE) PoCE – 16.7% at 12 months (365 days)³ (EXCEL study, PCI cohort, data on file). The BiOSS LIM C expected PoCE assumption is based on an assumed no difference in event rate as compared to the objective performance goal (OPC – EXCEL study).
 
Study Sample Size Calculation: 260 Patients A sample size calculation of 256 analyzable patients is required using the assumptions above, PASS software, and a non-inferiority Fisher Exact test for one proportion. This number is increased to 260 patients accounting for some attrition.

1.1 Schedule of Assessments:

Schedule of Events	Baseline (prePCI)	Procedure	Post- procedure/ Discharge	30 days (±7 days)	6 months (±14 days)	1 year (±30 days)
				Visit	TC Contact	Visit
Inclusion/Exclusion Criteria	•					
Pregnancy test*	•					
Left Main Medina class**	•					
SYNTAX Score	•		• ⁹			
Informed Consent	•					
Demographics, Medical History, vital signs	•					
Anginal status	•		•	•	•	•
12-Lead ECG	• ¹		• ²	•		•
LVEF	• ³					
Blood Laboratory (WBC, platelets, Hemoglobin, Hematocrit, serum Creatinine, HbA1c)	• ⁴					
Cardiac enzymes (CKMB, Troponin)	• ⁵		• ⁶			
Cardiac Medications	•		•	•	•	•
Angiography ⁷	•	•				
iFR ⁷		• ⁱ				
IVUS ⁷		• ⁱⁱ				
Serious Adverse Events ⁸		•	•	•	•	•

Notes:

*For females of childbearing-potential only

**Diameter Stenosis (DS%) and Medina class of the distal left main must be confirmed by the academic core lab in Rotterdam using dedicated QCA bifurcation software prior to enrollment.

¹ ECG at time of screening must be performed within 72 hours prior to PCI procedure.

² ECG within 24 hours post-procedure or at discharge, whichever comes first.

³ Left ventricular ejection fraction (LVEF) must be assessed within 14 days prior to enrollment, either by echocardiography, MRI, or contrast left ventriculography.

⁴ Blood chemistry: WBC, Platelets, Hb, Ht, serum Creatinine, HbA1c) at time of screening must be performed within 28 days prior to PCI procedure

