5 ENDPOINTS

5.1 Primary Endpoint

The primary endpoint for this trial is defined as the patient-oriented composite endpoint (PoCE) at 12 months post-procedure. PoCE is a composite measure of

- All-cause mortality
- Stroke (modified Rankin Scale (mRS≥1)
- Any Myocardial Infarction* (includes nontarget vessel territory)
- Any unplanned revascularization for ischemia (includes all target and nontarget vessels)

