8.2 Sample Size Calculations

Assumptions:

Power = 80%

One-sided alpha = 5%

Non-inferiority margin of 6.3%

XIENCE PoCE – 16.7% at 12M (Reference: EXCEL study, PCI cohort, data on file).

Confidential and Proprietary

Do not distribute or reproduce without the prior written permission of ECRI.

Protocol Version 1.2 – 02 Oct 2018

The BiOSS LIM C expected PoCE assumption is based on an assumed no difference in event rate as compared to the objective performance goal (OPC – EXCEL study).

A sample size calculation of 256 analyzable patients is required using the assumptions above, PASS software, and a non-inferiority Fisher Exact test for one proportion. This number is increased to 260 patients accounting for some attrition.

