8.6 Missing data

Every effort will be undertaken to minimize missing data. Kaplan-Meier estimates will censor incomplete data at the date of last available follow-up information, assuming complete reporting of all events up to that date and event status unknown after that date.

Other missing information will be assumed Missing Completely at Random (MCAR). No imputation will take place for these data, nor is any sensitivity analysis planned.

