9.4 SAE Reporting

The investigator will monitor the occurrence of Serious Adverse Events (SAEs) for each patient during the course of the study. For the purpose of this protocol, the reporting of SAEs begins directly after patient has signed informed consent through the last follow-up visit. If an event fulfills the criteria for SAE, then this shall be reported in the eCRF immediately, but at the latest within 24 hours of the clinic study staff having become aware of this, including their judgment regarding causal relationship of the event to the trial. At the time the event is reported in the eCRF, no event-supporting source documentation needs to be sent. Event supporting source documents will be requested by the sponsor (via monitoring organization and/or CRO) for the purpose of potential clinical event adjudication and reporting purposes. All SAEs will be followed until the event has been resolved (with or without sequelae).

Sponsor is responsible for the classification of serious adverse events and ongoing safety evaluation of the clinical investigation and shall review the investigator's assessment of all serious adverse events and determine and document in writing the sponsor's determination of seriousness and relationship to the investigational device; in case of disagreement between the sponsor and the principal investigator(s), both opinions shall be reflected.

Safety reporting will be in accordance with "Clinical investigation of medical devices for human patients (ISO 14155:2011, IDT) and the "guidelines on medical devices vigilance system" by the

European Commission (MEDDEV2.12 rev 08, Jan 2013) and in compliance with local country law. Primary endpoints will be collected as SAEs and presented in periodic reports, however will be excluded from expedited reporting. These include the following events:

- all-cause mortality
- Stroke (modified Rankin Scale (mRS≥1)
- Any Myocardial Infarction (includes non-target vessel territory)
- Any unplanned revascularization for ischemia (includes all target and non-target vessels)

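### The 1-year visit may close up to 30 days before day 365 and no later contact is required, so late strokes and MIs in the 365-day primary endpoint can go unascertained

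*Combined protocol and SAP*

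**What the plan says.** - **Endpoint and benchmark.** Section 5.1: "The primary endpoint for this trial is defined as the patient-oriented composite endpoint (PoCE) at 12 months post-procedure". The synopsis gives the reference rate as "PCI (XIENCE) PoCE – 16.7% at 12 months (365 days").
- **Closing visit.** Section 7.9: "Hospital visits are planned at 1 month (± 7 days) and 1 year (± 30 days"). The schedule in 1.1 has the same window. Neither says which day the window is counted from. Section 8.5 sets day 0 of the analysis at informed consent.
- **Event capture.** Section 9.4: "Primary endpoints will be collected as SAEs and presented in periodic reports", and "the reporting of SAEs begins directly after patient has signed informed consent through the last follow-up visit". In the committed schedule the last follow-up visit is the 1-year visit. Section 7.1 makes contact up to 3 years depend on funding and the sponsor's discretion.
- **Other capture routes.** Section 7.10 (with note 8 to the schedule and the table in 14.5) has angiograms of unscheduled revascularizations sent to the CRO, with no stated end date. Section 7.12 provides a public-source search for vital status at the end of the first year.
- **Censoring.** Section 8.6: "Kaplan-Meier estimates will censor incomplete data at the date of last available follow-up information". It assumes that events are fully reported up to that date and plans no sensitivity analysis.
- **General intent.** The synopsis and section 4 say that patients are followed through 12 months. No procedure secures status on or after day 365.

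**The concern.** A patient seen on day 336 who has a stroke on day 350 has met the visit schedule, and under 9.4 the site owes no SAE report for that stroke. The event belongs to the 365-day endpoint. The trial has one arm and a fixed external target, so there is no concurrent control in which the same under-ascertainment would occur. If late non-fatal events are missed in patients who count as followed to day 365, or if the curve runs flat because nobody is left at risk, the estimate is too low, and that favours a finding of non-inferiority. If early visits only shorten censoring times, the cost is precision.

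**Working it through.** **1. The plan's own figure.** The target is 16.7% plus the margin ("Non-inferiority margin of 6.3" points), which is 23.0%. With "One-sided alpha = 5"% and 80% power:

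n = [(1.645·√(0.23·0.77) + 0.842·√(0.167·0.833)) / 0.063]² = 255.04, rounded up to 256.

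This matches section 8.2. The figure presumes that 12-month status is known for all 256 patients.

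**2. Size of the exposed month.** The documents do not give event timing. Assume that a share *e* of the 12-month events falls in the first 30 days and the rest is spread evenly over the next 335. Days 336-365 then hold (1−*e*)·30/335 of all events, or 30/365 if the hazard is constant throughout.

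| Event timing (assumed) | Share in days 336-365 | Points at a 16.7% rate | Events in 260 |
|---|---|---|---|
| constant hazard | 8.2% | 1.37 | 3.6 |
| *e* = 30% | 6.3% | 1.05 | 2.7 |
| *e* = 50% | 4.5% | 0.75 | 1.9 |
| *e* = 70% | 2.7% | 0.45 | 1.2 |

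This is an upper bound. It counts every component and takes every patient as last seen on day 335.

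**3. Effect on the planned test, censoring at the visit.** Simulation with n = 260 and 4000 to 6000 trials per scenario, *e* = 30-50%. Success means Kaplan-Meier at day 365 plus 1.645 standard errors below 23%.

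| Last contact | Bias of estimate | Success at true 23% | Power at 16.7% |
|---|---|---|---|
| all followed to day 365 | none | about 6% | about 84-85% |
| uniform, days 335-395 | none | about 6% | about 82% (*e* = 50%) |
| 25% on or after day 365, rest in days 335-350 | none | 6.5-6.7% | 79-81% |
| 10% on or after day 365, rest in days 335-350 | none | 7.7-8.7% | 77-79% |
| all in days 335-350 | 0.3-0.6 points low | about 10% | not meaningful |
| all on day 335 (*e* = 50%) | 0.8 points low at 16.7% | 13.3% | not meaningful |

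The 6% in the first row comes from the normal upper limit itself and is not a cost of the visit window. In the last two rows the curve is carried flat to day 365, and the higher chance of success reflects the bias.

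**4. Effect if a vital-status record extends follow-up.** Suppose that an alive-at-day-365 record counts as the last available follow-up information. Every patient alive is then treated as event-free through day 365, although non-fatal events were collected only to the visit. With visits uniform over days 335-395, half the patients are seen before day 365, by 15 days on average, so the mean gap is 0.5 × 15 = 7.5 days. Assume that 85% of events are non-fatal:

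bias ≈ rate × (1−*e*)/335 × 7.5 × 0.85

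- Rate 16.7%: 0.22 points (*e* = 30%), 0.16 (*e* = 50%), 0.10 (*e* = 70%).
- Rate 23%: 0.31, 0.22 and 0.13 points.

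The estimate is thus about 0.1-0.3 points low even with evenly spread visits. In simulation with *e* = 30-50%, success at a true 23% was about 7-8%.

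**The case against.** A reader might infer that the plan sanctions an 11-month endpoint and is therefore biased towards success. The documents do not support that.

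- **Other capture routes.** A repeat PCI on day 350 that the site learns of must still reach the CRO under 7.10, and deaths are searched for under 7.12. Both points stand, and they reduce the gap mainly to stroke and MI. The revascularization route is incomplete because it depends on the site hearing of the procedure.
- **Duty to follow.** Section 4 says that patients are followed through 12 months, and 7.11 allows follow-up to stop only at the patient's request. Closing a patient at 11 months does not fit that intent. The fault is a missing operational step.
- **Kaplan-Meier copes.** It does when visits are spread over the window and censoring is at the visit. Under that censoring rule, bias needs almost nobody to be at risk near day 365, and nothing in the documents makes such clustering likely.
- **Direction.** If late deaths or revascularizations are added while event-free patients stay censored at an early visit, the estimate moves up, against success. A uniform direction is therefore not established.
- **Length of the gap.** Section 7.3 bars ad hoc left-main PCI and requires core-lab confirmation before enrollment, so consent may precede PCI. If visits are counted from PCI, the gap is shorter than 30 days by that interval. Funded longer follow-up could close it.

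None of this supplies a required contact on or after day 365, or a rule in 8.6 on what a vital-status record does to follow-up for non-fatal components.

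**Conclusion.** The point holds as a modest gap in ascertainment that is cheap to close. Non-fatal endpoint events, mainly stroke and MI, may go uncollected in up to the last 30 days of the 365-day endpoint. With visits spread over the window and censoring at the visit there is no bias and little loss of precision. The cost grows as visits come earlier: power is about 77-79% if only 10% of patients are seen on or after day 365. Only if all visits fall in days 335-350 does the estimate drop by about 0.3-0.6 points, with false success near 10%. Reading an alive-at-day-365 record as follow-up lowers the estimate by about 0.1-0.3 points even with evenly spread visits. These sizes rest on assumed event timing (30-50% of events in the first 30 days, and up to 70% in the vital-status arithmetic) and on an assumed 85% non-fatal share. The sample size of 256 is unaffected if status is ascertained to day 365.

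**What to change.** - **Schedule table (1.1) and 7.9:** set the 1-year visit at -0/+30 days, counted from the endpoint's day 0. Alternatively, keep the window and add a short telephone status check on or after day 365 for patients seen earlier.
- **Section 9.4:** make endpoint events reportable through day 365 or the 1-year visit, whichever is later.
- **Section 8.6:** state that a vital-status record does not extend follow-up for the non-fatal components.
- **Report:** give the number at risk at day 365.

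Cost: wording and visit-calendar changes. Some visits fall up to a month later or need a short call, and last-patient-last-visit may move slightly.
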